### **Study Aims and Hypotheses**

The goals of the study will be as follows:

- 1. To examine the perceived acceptability, usefulness, and client satisfaction following participation in the Single-Session Consultation (SSC) service at the Krasner Psychological Center (KPC) and Mind Body Clinical Research Center (MBCRC) among waitlisted adolescent and adult clients
- 2. To examine therapists' perceived acceptability, feasibility, and effectiveness of the single session consultation at three time points: pre-training, post-training, and post-SCC administration
- 3. To assess the demand for and feasibility of providing the SSC service at the Krasner Psychological Center and Mind Body Clinical Research Center (i.e., documenting the proportion of clients who choose to participate in the service when it is offered; documenting the number of sessions successfully completed, rescheduled, and/or cancelled).
- 4. To assess whether levels of proximal clinical outcomes (e,g, hope, agency) are improved immediately following completion of the SSC, both in adolescent and adult clients.
- 5. To assess whether levels of psychological symptoms are improved two weeks following completion of the SSC, both in adolescent and adult clients.
- 6. To assess rates of (a) remaining on the clinic waitlist for therapy and (b) length of subsequent treatment at the Mind Body Clinical Research Center and Krasner Psychological Center among individuals participating in the SSC, relative to clients who sought out services in the six months prior to the SSC being offered to clients (January June 2019).

Hypotheses associated with each of these aims will be as follows:

- 1. Clients' proximal clinical outcomes (e,g, hope, measured by the Beck Hopelessness Scale 4 item version, and Agency, measured by the State Hope Scale; both primary study outcomes), which are hypothesized to serve as mechanisms for intervention effects, will improve from immediately pre-SSC completion to immediately post-SSC.
- 2. Adolescent and adult clients will perceive the SSC at the Mind Body Clinical Research Center and Krasner Psychological Center as acceptable and useful in addressing their clinical needs, indexed by mean ratings of at least 3.5 out of 5 across the five items on the "Consultation Feedback Form".

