- 3. The SSC will show feasibility as a model for service provision at the Mind Body Clinical Research Center and Krasner Psychological Center (i.e., a majority [>50%] of clients who are offered the SSC service will elect to receive it, and most [>75%] of clients who schedule an SSC appointment will attend)
- 4. Clients' overall psychological symptom levels will reduce two weeks after the SSC, relative to symptoms immediately prior to the SSC

- 5. No prediction is made about therapists' perceived acceptability, feasibility, and effectiveness of single session interventions at baseline or their subsequent assessment, given the novelty of research in this domain.
- 6. Clients who receive the SSC will be less likely to remain on the clinic wait list—and, among those who elect to remain on the clinic wait list, total therapy duration will be briefer—relative to clients who sought service at the Mind Body Clinical Research Center and Krasner Psychological Center prior to the SSC service being offered.

Note that data will be available for testing hypotheses 1-5 substantially sooner than for testing hypothesis 6, as the duration of clients' potential future psychotherapy at the Krasner Psychological Center and Mind Body Clinical Research Center is impossible to determine. Whereas data for the first four hypotheses will be available two weeks subsequent to recruitment completion, data for the fifth hypothesis may be unavailable for up to a year subsequent to recruitment completion. Accordingly, the authors may report results from hypotheses 1-5 in a manuscript or conference presentation prior to completion of data collection for hypothesis 6, noting that data relevant to hypothesis 6 will be reported at a to-be-determined future date. Data relevant to hypothesis 6 (which requires extraction of aggregate client information associated with previous Mind Body Clinical Research Center and Krasner Psychological Center clients) will not be collected, and thus will remain unknown to investigators, until all relevant data are available for analysis (i.e., until all clients who completed the SSC and chose to receive full-length psychotherapy have terminated their course of treatment at the clinic).

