To address our fifth research question (for which no hypotheses are proposed), we will aggregate descriptive statistics from the "Therapist Beliefs about SSC" scales and will compare the scales between (1) pre-training and post-training and (2) post-training and post-SSC administration. Positive perceptions of the SSC at any given time-point will be defined by a mean rating of at least 3.5 out of 5 across all items; less-than-positive perceptions will be defined by a mean rating of less than 3.5 out of 5 across all Likert scale-rated items. We will report all qualitative data collected via this measure—specifically, we will report therapists' written responses to openended questions about their perceptions of the SSC. Because the scope and amount of this qualitative data are likely to be limited, and given the exploratory nature of the present study, we do not intend to conduct any formal qualitative data analyses in this study.

To address Hypothesis 6, we will conduct two 2-tailed independent-samples t tests. First, we will assess whether the percentage of individuals removing themselves from the clinic's waitlist after completing the SSC differs from the percentage of individual who had removed themselves from the waitlist in the six months prior to the SSC's being offered at the clinic. A difference with a p value of < .05, with a higher value for the SSC group, would suggest that individuals who receive the SSC may be more likely to voluntarily remove themselves from the clinic waitlist than individuals who had not received the SSC in the past. Second, we will calculate the mean number of psychotherapy sessions completed at the Mind Body Research Clinical Center and Krasner Psychological Center among individuals who receive the SSC and elect to remain on the clinic's waitlist. We will then test whether this mean number of sessions differs from the mean

number of sessions completed by clients who began psychotherapy in the six months prior to the SSC's being offered at the clinic. A difference with a p value of < .05, with a lower value for the SSC group, would suggest that individuals who receive the SSC may be more likely to have a shorter course of psychotherapy than those who do not receive the SSC prior to full-length treatment. Note that for both of our Hypothesis 6 analyses, we will restrict our sample of previously-seen clients to those in the same age-range as in the study sample, in order to optimize comparability between groups.

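### The second Hypothesis 6 test compares therapy length only among clients who stay on the waitlist after the SSC, so it carries selection bias of unknown direction and cannot support a conclusion about all SSC recipients

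*SAP*

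**What the plan says.** Hypothesis 6 has two parts. The first is that "Clients who receive the SSC will be less likely to remain on the clinic wait list" than earlier clients. The second is that, "among those who elect to remain on the clinic wait list, total therapy duration will be briefer". Aim 6 is not limited in this way: it asks about "length of subsequent treatment at the Mind Body Clinical Research Center and Krasner Psychological Center among individuals participating in the SSC".

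The Analytic Plan states that "we will conduct two 2-tailed independent-samples t tests". The first compares the percentage leaving the waitlist. The second takes the average session count "among individuals who receive the SSC and elect to remain on" the waitlist and compares it, for the historical group, with the average "number of sessions completed by clients who began psychotherapy in the six months prior to the SSC's being offered at the clinic". The criterion for a favourable reading is "A difference with a p value of < .05, with a lower value for the SSC group", and such a result is taken as suggesting a shorter course of therapy for people who receive the SSC, compared with people who do not receive it before full-length treatment. The only step towards comparability is restriction of the earlier clients to the study's age range.

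**The concern.** The second test selects its SSC sample on something that happens after the SSC and that the first test treats as an SSC outcome. If the first half of Hypothesis 6 is true, the SSC clients who remain are a different selection of service-seekers from the earlier clients who went on to therapy. Their means can then differ even if the SSC alters nobody's course of therapy. Restricting by age does not address this.

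The second problem is one of definition. The SSC group is made up of people who choose to remain. The earlier group is made up of people who began therapy. A client who remains and never starts can enter the SSC mean as 0, but has no counterpart in the earlier mean.

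At stake is how either result is read. A lower mean could come from selection or from non-starters. A mean that is no lower could hide a real shortening. The stated conclusion concerns people who receive the SSC, and the test does not estimate that.

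**Working it through.** The SAP gives no leave rate, session count, SD or effect size for Hypothesis 6, so there is no figure of its own to reproduce. The client sample of 40 (Sample Size Justification) rests on pilot-study guidelines. Every session count and leave rate below is an assumption.

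**1. Two-class example.** Take 40 clients per group: 20 would use 8 sessions and 20 would use 24. The SSC changes no one's course. Ten low-need clients leave after the SSC, and five low-need clients left in the earlier period.

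- SSC clients who stay: (10×8 + 20×24)/30 = 560/30 = 18.7
- Earlier clients who began: (15×8 + 20×24)/35 = 600/35 = 17.1
- Conditional difference: 18.67 − 17.14 = +1.5 sessions
- All clients, leavers as 0: 560/40 − 600/40 = 14.0 − 15.0 = −1.0

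**2. Continuous model.** Would-be sessions are lognormal with mean μ = 16 and CV 0.8, so σ = √ln(1 + 0.8²) = 0.703. A normal score governs staying and has correlation ρ with log sessions. The lowest fraction p leaves: 30% after the SSC and 15% earlier. The SSC has no effect on anyone's sessions. Then

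- mean among those who stay = μ·Φ(ρσ − z_p)/(1 − p)
- mean over all clients, leavers as 0 = μ·Φ(ρσ − z_p)

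with z_0.30 = −0.524 and z_0.15 = −1.036. For ρ = 0.5, the SSC mean is 16×0.8095/0.70 = 18.50 and the earlier mean is 16×0.9174/0.85 = 17.27, a difference of +1.23. The all-client difference is 16×(0.8095 − 0.9174) = −1.73.

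| ρ | SSC, stay | Earlier, began | Conditional difference | All-client difference |
|---|---|---|---|---|
| −0.5 | 13.00 | 14.18 | −1.18 | −2.95 |
| −0.3 | 14.24 | 14.97 | −0.73 | −2.76 |
| 0 | 16.00 | 16.00 | 0.00 | −2.40 |
| 0.3 | 17.58 | 16.83 | +0.75 | −2.00 |
| 0.5 | 18.50 | 17.27 | +1.23 | −1.73 |
| 0.7 | 19.32 | 17.63 | +1.69 | −1.46 |

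Positive ρ means that low-need clients leave; negative ρ means that high-need clients leave. With no true effect on length, the whole conditional difference is bias.

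**3. Sensitivity to the model.** This is a simulation with gamma-distributed sessions (mean 12, SD 8) and 10% leaving earlier. With no true effect, the conditional difference runs from −1.15 (ρ = −0.5) to +1.79 (ρ = 0.8) when 30% leave after the SSC, and from −2.17 to +3.88 when 50% leave. It is about 0 when the leave rates are equal, and also when leaving is unrelated to need. With a true 15% shortening, 50% leaving and ρ = 0.5, it is +0.13, so the benefit disappears.

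**4. Definition mismatch.** In the model of step 2 with ρ = 0.5, suppose 10% of SSC clients who stay never start and count as 0. The SSC mean becomes 0.9×18.50 = 16.65, and the difference moves from +1.23 to 16.65 − 17.27 = −0.62. A small share of non-starters is enough to change the sign.

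**The case against.** The strongest defence is that the test matches its hypothesis. The conditional claim is written in advance, the first test covers those who leave, and the two can be read as a two-part analysis. The conclusion is hedged, and its contrast with full-length treatment points towards people entering therapy. Aim 6 is also weak support for the contrary view, since length of treatment has no natural value for someone who has none. This stands as a description of intent. It does not make the two groups comparable, and the conclusion is still worded for SSC recipients.

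A second defence is that the earlier group is restricted as well. That removes the bias only if the SSC does not change who remains, which is the opposite of what Hypothesis 6 predicts. It does reduce the size. A reader might set 18.7 against the unselected mean of 16 and see a gap of 2.7 sessions, but once five earlier leavers are allowed the gap is 1.5.

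A third is that the bias is small against the noise. With SD 12.8 (16×0.8), 28 SSC clients (70% of 40) and 34 earlier clients (85% of an assumed 40), the standard error is 12.8×√(1/28 + 1/34) = 3.3 sessions. In simulation with low-need clients leaving (ρ from 0.3 to 0.7), a significantly longer result appears in 5–8% of trials with 40 earlier clients and 6–13% with 200, against a nominal 2.5% and before the false-discovery step. This stands: a false significant finding would be uncommon. The bias still shifts the estimate, and a larger historical group does not remove it.

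Finally, an all-client mean answers a different question. It falls mechanically when more clients leave: 16×(0.70 − 0.85) = −2.4 with leaving unrelated to need and no effect on length. This also stands, and the fix has to respect it.

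**Conclusion.** The second Hypothesis 6 test conditions on a post-SSC choice that the plan expects the SSC to alter, and it defines its two groups differently. The resulting bias is of unknown direction. It is about −1.2 to +1.7 sessions under the assumed mean of 16, CV of 0.8, leave rates of 30% against 15%, and ρ between −0.5 and 0.7. It is wider if the leave rates differ more. The stated conclusion about people who receive the SSC does not follow from the test.

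A reader might infer that the test is biased against the SSC, so that the more clients it helps to leave, the longer therapy appears. The SAP does not support this. It does not say who leaves: the bias is about zero if leaving is unrelated to need, favours the SSC if high-need clients leave, and can be offset by non-starters counted as 0.

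The severity is modest. Hope and agency are the primary outcomes, the study is framed as a pilot, and a historical comparison is open to other confounding in any case. The change is still worth making, because the SAP attaches a significance rule and an effect conclusion to this test.

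**What to change.** 1. Make the main session comparison the number of later clinic sessions per client over all SSC recipients against all earlier service-seekers in the comparator period, in the same age range. Count leavers and non-starters as 0 in both groups. State that it measures total clinic use and is not evidence of a shorter course of therapy.
2. Keep the conditional comparison as descriptive. Define it the same way in both groups, as clients who began psychotherapy, and report it beside the two leave rates. Limit its conclusion to clients who start therapy, with no causal reading for all SSC recipients.

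The cost is mainly SAP wording. The waitlist-removal test already needs largely the same records, and the SAP says that Hypothesis 6 data will not be collected until all are available, so the change can precede sight of the data. The downsides are that the new outcome has many zeros, partly restates the leave rate, and does not capture care received elsewhere. If high-need clients leave for other providers, the all-client difference favours the SSC even more than the conditional one (−2.95 against −1.18 at ρ = −0.5), which is why it must be read only as use of these clinics.

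### Hypothesis 6 defines its two groups by different events: the session test sets SSC clients who stay on the waitlist against past clients who started therapy

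*SAP*

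**What the plan says.** Three parts of the SAP define the Hypothesis 6 comparison.

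- **Session test (Analytic Plan).** The SSC mean is taken "among individuals who receive the SSC and elect to remain on the" waitlist. The comparison is the mean "number of sessions completed by clients who began psychotherapy in the six months prior" to the SSC being offered. A significant difference with the lower mean in the SSC group is to suggest that SSC recipients may be more likely to "have a shorter course of psychotherapy than those who do not receive the SSC prior to full-length treatment".
- **Removal test (Analytic Plan).** The plan asks whether the percentage of people leaving the "waitlist after completing the SSC differs from the percentage of individual who had removed themselves from the waitlist in the six months prior" to the service. No end of follow-up is given for the SSC group, and no denominator or follow-up per client for the past group.
- **Past clients (Study Aims and Hypotheses).** Aim 6 uses "clients who sought out services in the six months prior to the SSC being offered to clients", dated January to June 2019. Hypothesis 6 says "among those who elect to remain on the clinic wait list, total therapy duration will be briefer", "relative to clients who sought service at the Mind Body Clinical Research Center" and the second site before the service existed.

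The one comparability step stated for both tests is to "restrict our sample of previously-seen clients to those in the same age-range as in the study sample".

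**The concern.** Staying on a waitlist and beginning therapy are different events. The session test conditions on the first in the SSC group and on the second in the past group. An SSC client who stays listed but never has a session belongs to the SSC group as written and contributes a zero. A past client with the same history is excluded by definition. The difference can only lower the SSC mean, which is the direction that the plan reads in favour of the SSC.

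The past group also changes between sections: people who sought service in the aim and the hypothesis, people who began therapy in the session test. In a clinic with a waitlist these are not the same people.

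For removal, a percentage counted over an open-ended period could be set against one counted over six months. Longer follow-up gives more removals whether or not the SSC does anything.

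**Working it through.** The SAP gives no rate, SD, effect size or past-group size for Hypothesis 6, so there is no stated figure to reproduce. From the document come the 40 SSC clients, recruitment from October 2019 to about May 2020, Hypothesis 6 results by May 2021, the January-June 2019 period, two-sided t tests at p < .05, and the FDR rule. Everything else below is assumed. All calculations suppose no SSC effect, so the nominal chance of a significant result favouring the SSC is 2.5%.

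**1. Sessions, literal reading.** Let m and s be the mean and SD among clients who start, and q the share of SSC remainers who never start.

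- SSC mean = (1 - q)m
- SSC variance = (1 - q)(s² + m²) - [(1 - q)m]²

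With m = 12, s = 8 and q = 0.20:

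- SSC mean = 0.8 × 12 = 9.6, against 12, a difference of 2.4.
- Variance = 0.8 × (64 + 144) - 9.6² = 166.4 - 92.16 = 74.24.
- With 30 v 30, SE = √(74.24/30 + 64/30) = 2.147.
- Chance of a false benefit ≈ Φ(2.4/2.147 - 1.96) = Φ(-0.84) ≈ 20%.

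A simulation gives the range: pooled t tests, 20,000 runs, sessions as 1 + negative binomial with mean 12 among starters, 20 to 38 SSC clients v 40 to 100 past clients.

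| SSC remainers who never start | False benefit, SD 8 | False benefit, SD 12 |
|---|---|---|
| 0% (starters only in both groups) | 1.8-2.5% | 1.3-2.5% |
| 3% | 3-4% | 2-3% |
| 5% | 4-6% | 3-4% |
| 10% | 8-12% | 5-7% |
| 20% | 19-35% | 11-19% |
| 30% | 37-63% | 21-37% |

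The SAP names five t tests (two for Hypothesis 1, one for Hypothesis 4, two for Hypothesis 6), so the strictest Benjamini-Hochberg cut is 0.05/5 = 0.01, nominally 0.5% on the favourable side. At that cut, with 10%, 20% and 30% never starting, false benefit is 2-4%, 7-16% and about 18-40% (SD 8), and 1-2%, 3-6% and 7-16% (SD 12). With 3-5% never starting it is at most 1.3%.

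**2. Sought v began.** Assume a steady state with monthly rates of self-removal H = 0.03 to 0.08 and of therapy start S = 0.15 to 0.30, and L = H + S. Among clients who begin therapy in a six-month period, the share who sought service before it is (1 - e^(-6L))/(6L).

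- L = 0.18: (1 - e^(-1.08))/1.08 = 61%
- L = 0.38: (1 - e^(-2.28))/2.28 = 39%

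So about 39-61% of the past session group would lie outside the Aim 6 cohort. This counts different people. It shows no direction of bias in mean sessions.

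**3. Removal.** With therapy start as a competing exit, cumulative removal by month t is H/(H + S) × (1 - e^(-(H+S)t)). Take H = 0.05 and S = 0.15 as an example.

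- *The six months date the cohort.* Followed to May 2021, SSC clients have 12-19 months and past clients 23-28 months. Expected removal is 23.8% v 24.8%. Over all the rates, with 40 v 80 to 150 clients, false benefit is 2-3%.
- *The six months date the removals.* With 12 months v a full 6 months, expected removal is 22.7% v 17.5%, and false benefit over all the rates is 4-14%. With 12 months v staggered entry giving 0-6 months, it is 22.7% v 10.4%, and false benefit is about 12-64%.

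**The case against.** The strongest reply is that therapy recipients are meant in both groups. Hypothesis 6 speaks of therapy duration, the outcome is psychotherapy sessions completed, and the planned conclusion concerns a course of psychotherapy. The section on aims also holds back extraction until the SSC clients who opted for full-length therapy have finished it. On that reading there is no inflation. This stands as a plausible account of intent. But that sentence says when the data will be ready, while the sentence that defines the analysis group does not require a first session.

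The never-start share has no source in the document. If waitlist status is taken at the late extraction, people who give up waiting count as removals, and few never-starters would be left among the remainers. The low rows of the table then apply.

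A reader might infer three stronger things, and the SAP supports none of them.

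- *The session test as planned has a false-positive rate of 20-60%.* That needs both the literal zero-session reading and an assumed share of 20-30%.
- *The removal test is badly biased.* Aim 6 dates the cohort by when clients sought service, and on that reading the error stays near nominal. The large figures need Aim 6 to be set aside.
- *Sought v began biases the session mean.* Only a difference in who is included is shown.

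It is also fair that Hypothesis 6 is not primary, is non-randomised, is hedged in its wording, and falls under the FDR rule. The FDR rule lowers the figures but cannot correct a comparison of groups defined by different events.

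**Conclusion.** The point holds as an inconsistency within the SAP. The session test conditions on different events in its two groups, and its past group is not the one named in Aim 6 and Hypothesis 6. Followed literally, it favours the shorter-course conclusion. With no SSC effect, false benefit against a nominal 2.5% is about 2-6% if 3-5% of remainers never start, 5-12% if 10%, 11-35% if 20% and 21-63% if 30%. These figures rest on assumed session distributions, group sizes and never-start shares. If only starters are meant, there is no inflation.

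The removal test lacks a common follow-up. This matters little if the six months date the cohort, as Aim 6 indicates. Severity is minor to moderate, and the results for the other hypotheses are unaffected.

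**What to change.** Amend the Hypothesis 6 paragraph of the Analytic Plan before the data are extracted. The SAP collects these data last, so the rules can still be set without knowledge of them.

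1. **One past group for both tests:** the Aim 6 cohort, that is, clients who sought services in its six-month period at the two sites, in the same age range.
2. **Sessions:** include only clients with at least one therapy session in both groups, count sessions to termination in both, and report the never-started share of each group beside the means.
3. **Removal:** use the same follow-up length in both groups, for example 6 months. State the start date and the denominator for each group, and report the difference in percentages with a 95% CI.

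A 6-month window for clients recruited in about May 2020 ends in about November 2020, so it fits the May 2021 report.

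Costs:

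- Restricting to starters conditions on an event that the SSC may itself affect, so the comparison stays descriptive.
- Removals after the window are not counted.
- The start dates of the two groups cannot be matched perfectly, since past clients have no SSC date.
- The SAP plans to extract aggregate information on past clients. The request must therefore ask for aggregates cut to these rules, or for client-level dates.

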# **Sample Size Justification**

We are primarily interested in obtaining precise estimates of feasibility and acceptability outcomes; client satisfaction ratings; and changes in possible change mechanisms (hope, agency), which will aid in the planning of a larger-scale efficacy trial. A client sample size of 40 from two outpatient sites will allow us to be relatively precise in our conclusions regarding feasibility outcomes, as well as change in hope and agency scores from pre-to-post-intervention, based on guidelines for pilot study planning proposed by Joulius (2005) and Whitehead et al (2016).

We will also recruit therapists to take part in this study. Specifically, all therapists attending the initial training will be offered the opportunity to voluntarily and anonymously complete a questionnaire on their perceptions of the single-session consultation program. Since we have no way of knowing how many therapists will choose to participate in this study, the sample size for therapist participants is unknown. Therapist data will be exploratory, serving as pilot data for potential future studies.

Note: the trial initially recruited three outpatient centers (Krasner Psychological Center, Mind Body Clinical Research Center, and Child Adolescent Outpatient Services). Due to logistical and administrative issues encountered at the Child Adolescent Outpatient Services during study set up, this site was excluded. Based on the ongoing recruitment rates at the two remaining sites, the sample size of 40 is feasible to recruit.

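### Restricting past clients to the study's age range leaves the adolescent/adult mix uncontrolled in Hypothesis 6; both comparisons should be stratified or adjusted by age group

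*SAP*

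**What the plan says.** The first aim in Study Aims and Hypotheses sets the client population: the SSC is studied "among waitlisted adolescent and adult clients". No numeric age limits are given. The sixth aim looks at waitlist status and length of later treatment "relative to clients who sought out services in the six months prior to the SSC being offered to clients", that is, January to June 2019. Recruitment to the SSC is projected from October 2019 (Study Timeline).

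For this comparison the Analytic Plan states "we will conduct two 2-tailed independent-samples t tests", one for the percentage leaving the waitlist and one for the number of therapy sessions. The session test keeps only those SSC clients who choose to stay on the waitlist. For both tests the plan adds that it will "restrict our sample of previously-seen clients to those in the same age-range as in the study sample, in order to optimize comparability". Beyond drawing both groups from the same two clinics, this is the only comparability measure. No matching, stratification, weighting or covariate is named. The past-client data are described as an "extraction of aggregate client information associated with previous Mind Body Clinical Research Center and Krasner Psychological Center clients".

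**The concern.** By adding the restriction, the SAP treats age as a threat to a non-randomised before-after comparison. A common range deals with one part of that threat, namely clients of ages not represented in the study. It does not deal with the other part, which is how many adolescents and how many adults each group contains.

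The mix could differ for reasons visible in the SAP. SSC clients are those who accept the offer, and the feasibility threshold is only more than 50% acceptance. The session comparison selects again on staying on the waitlist. Past clients pass through no SSC uptake filter, and the calendar periods differ.

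If the mix does differ, and adolescents and adults differ in waitlist removal or number of sessions, the age difference enters both tests unadjusted. The SAP attaches a significance criterion and a directional interpretation to each test, for example "A difference with a p value of < .05, with a higher value for the SSC group" for waitlist removal. A difference in age mix could therefore be read as an SSC effect, or could mask a real one.

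**Working it through.** The SAP gives no figure on this point (no age distribution, adolescent share, number of past clients or power for Hypothesis 6), so there is nothing to reproduce. The argument is logical, and the numbers below only illustrate it.

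**Inputs from the SAP**
- Population: adolescents and adults (Study Aims and Hypotheses).
- SSC sample: "A client sample size of 40 from two outpatient sites" (Sample Size Justification).
- Tests: two-sided, p < .05, with a Benjamini-Hochberg requirement of q < 0.05 applied as well (Analytic Plan).

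**Inputs assumed**
- Adolescent shares, outcome gaps, number of past clients and standard errors.

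**Step 1: what the restriction does.** Suppose the age range is the observed minimum to maximum of n SSC clients, and past clients have the same continuous age distribution. The expected share of past clients kept is then (n − 1)/(n + 1).
- n = 40: 39/41 = 95.1% kept, 4.9% removed.
- If the clinics also saw children younger than any study client, with assumed share c, the share removed is c + (1 − c) × 2/41. This is 14%, 24% and 33% for c = 10%, 20% and 30%.

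In every case the adolescent/adult ratio among those kept is whatever it happens to be. The same is true if the age range means an eligibility range.

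**Step 2: bias from mix.** With no SSC effect, the expected difference (SSC minus past) is (adolescent share in SSC − adolescent share in past) × (adolescent value − adult value).
- Sessions, shares 50% v 20%, means 8 v 14: SSC mean 0.5 × 8 + 0.5 × 14 = 11.0; past mean 0.2 × 8 + 0.8 × 14 = 12.8; difference (0.5 − 0.2) × (8 − 14) = −1.8 sessions.
- Same means, shares swapped (20% v 50%): +1.8 sessions, so the SSC looks longer.
- Equal shares: 0.
- Waitlist removal 20% in adolescents and 40% in adults, shares 20% v 40%: (0.2 − 0.4) × (0.2 − 0.4) = 4 points. Shares 20% v 60%: (0.2 − 0.6) × (0.2 − 0.4) = 8 points.

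**Step 3: effect on error rates at raw p < .05, no SSC effect**
- Waitlist removal, 40 v 100 clients (100 assumed): the 4- and 8-point differences give a significant result in that direction about 7% and 16% of the time, against 2.5% without bias.
- Sessions, simulated t test, 30 v 100 clients (both assumed), 20,000 runs, two-sided rejection:

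| Adolescent-adult gap | Shares 30% v 30% | Shares 20% v 40% | Shares 20% v 60% |
|---|---|---|---|
| 0.3 SD | 0.048 | 0.060 | 0.085 |
| 0.5 SD | 0.050 | 0.072 | 0.146 |
| 0.8 SD | 0.048 | 0.109 | 0.303 |

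- For the 1.8-session scenario with an assumed standard error of 1.7 to 2.3 sessions, the chance of a falsely shorter result is Φ(−1.96 + 1.8/SE): 0.18 at 1.7 and 0.12 at 2.3, against 0.025 without bias.

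**Step 4: with the false discovery rate step.** The client t tests number five: two under Hypothesis 1, one under Hypothesis 4 and two under Hypothesis 6. A lone significant result must then meet 0.05/5 = 0.01. In the 1.8-session scenario the chance becomes Φ(−2.576 + 1.8/SE): 0.065 at SE 1.7 and 0.036 at SE 2.3, against 0.005 without bias. If other tests are also significant, the rate lies between these values and those in Step 3.

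**The case against.** The strongest reply is that the SAP does not show any imbalance. Past and SSC clients come from the same two clinics, and nothing says their age mix differs. Each illustration rests on shares and gaps that were chosen, and with the shares reversed the bias runs against the SSC. This stands: the documents show that the mix is uncontrolled, not that it is unequal.

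Stronger readings that the documents do not support:
- A reader might infer that the restriction excludes almost no one. The 95.1% figure assumes the observed range is used and that the two groups have the same ages. Under that same assumption the mix is equal and the bias is zero. If the clinics saw younger children, the restriction removes considerably more and is useful. The SAP does not say which holds.
- A reader might infer that the adolescent share in the SSC sample is large. Nothing supports that; the Child Adolescent Outpatient Services site was in fact dropped.
- A reader might infer that the SAP declares age dealt with. It states a purpose for the restriction, claims neither balance nor adjustment, and words its Hypothesis 6 conclusions cautiously.
- A reader might take 12% to 18% as the false-positive rate. That is one scenario before the false discovery rate step. That step limits multiplicity; it does not remove the bias.

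It is also fair that Hypothesis 6 is a later-reported, non-randomised comparison in a pilot whose sample size was justified on other outcomes, and that age is only one way in which the two periods may differ. This limits the weight of the point. None of it changes the fact that a range spanning both age groups cannot equalise their proportions.

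**Conclusion.** The point holds in a limited form. The one stated comparability step trims ages outside the study range and leaves the adolescent/adult mix uncontrolled in both unadjusted Hypothesis 6 tests. Bias arises only if two conditions hold together: the mix differs between SSC and past clients, and the age groups differ in waitlist removal or therapy length. The SAP informs neither, so size and direction are unknown. The assumed cases run from no bias to 1.8 sessions in either direction, or 4 to 8 percentage points in waitlist removal. The weakness is modest given the role of Hypothesis 6, but it is worth correcting because a better analysis is available and the SAP defers collection of the past-client data.

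**What to change.** - Keep the age-range restriction, and say whether it means the observed or the eligible range.
- Extract past-client data at client level or, failing that, separately for adolescents and adults: numbers on and removed from the waitlist, and number, mean and SD for sessions.
- Compare waitlist removal stratified by adolescent/adult, for example by Mantel-Haenszel.
- Compare session counts stratified by, or adjusted for, age group. A continuous age covariate requires client-level data.
- Report the adolescent share in each group, and soften the comparability claim to say that the restriction limits the age range only.

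The cost is more than wording. Pooled totals would not suffice, so the extraction described as aggregate must be broken down by age group. Stratification also costs a little precision. For illustration, take 20 adolescents and 20 adults in the SSC group, 40 and 160 among past clients, and a common SD within age groups. The effective size is then 20 × 40/60 + 20 × 160/180 = 31.1, against 40 × 200/240 = 33.3 unstratified. The standard error is larger by a factor of √(33.3/31.1) ≈ 1.035, about 3.5%.
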